10.4.13 Treatment Satisfaction Questionnaire for Medication-9 Items (TSQM-9)

The TSQM-9 is a 9-item measure that assesses the most common dimensions patients use to evaluate their medication (ie, global satisfaction, effectiveness, and convenience).⁴⁶ The results for each scale are presented from 0 to 100, where higher scores represent better satisfaction. TSQM-9 responses will be captured from the patient as outlined in the SoA (Table 1).

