11.8.2 Analysis of Quality of Life Endpoints

The Quality of Life (QoL) endpoints of Total DLQI and CDLQI will be analysed in the same way as the continuous other secondary efficacy endpoints occurring at multiple post-Baseline visits on the overall population.

DLQI-R, RECAP, TSQM-9, and WHO-5 will all be analysed descriptively on the overall population. Any individual components related to QoL scoring will also be analysed descriptively for the overall population.

All QoL endpoints and related individual components will also be analysed descriptively for the Maintenance Period, presented by treatment group as randomised during the Induction Period.

11.8.3 Analyses of Endpoints Related to the Secondary Objective (From Week 16 to Week 52)

All variables described in [Table 3](#) from [Section 6](#) will be analysed by means of descriptive statistics overall and separately, considering the arm where they were randomized during the induction period. More detailed description will be provided in the SAP.

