World Health Organisation – Five Well-Being Index (WHO-5)	
The WHO-5 is a short, self-administered measure of well-being over the last two weeks. It consists of five positively worded items that are rated on 6-point Likert scale, ranging from 0 (at no time) to 5 (all of the time). The raw scores are transformed to a score from 0 to 100, with lower scores indicating worse well-being. A score of ≤50 indicates poor wellbeing and suggests further investigation into possible symptoms of depression. A score of 28 or below is indicative of depression.
	Change from Baseline WHO-5 by week up to Week 16	
Total raw score calculated as the sum of all raw scores. The total raw score (ranging from 0 to 25) is then multiplied by 4 to get the transformed total score between 0 and 100.
 
Change calculated for each post-baseline assessment as:
 $\text{observed WHO-5 transformed total score} - \text{baseline WHO-5 transformed total score}$	None

This document is confidential.

Measure	Description	Variable	Derivation / Comment	Imputation Approach if Missing Components
Treatment Satisfaction Questionnaire for Medication-9 items (TSQM-9)	Version 9 of the TSQM consists of 9 items that results in three specific domains: Effectiveness, Convenience, and one global scale item, Global Satisfaction. Scores for each domain are computed by adding the TSQM items in each domain and then transforming the composite score into a value ranging from 0 to 100.	EFFECTIVENESS	$\frac{((\text{Item 1} + \text{Item 2} + \text{Item 3}) - 3)}{18} * 100$	If one item is missing $\frac{((\text{Sum}(\text{Item 1?} + \text{Item 2?} + \text{Item 3?})) - 2)}{12} * 100$
		CONVENIENCE	$\frac{((\text{Sum}(\text{Item 9 to Item 11}) - 3)}{18} * 100$	If one item is missing $\frac{((\text{Sum}(\text{Item 9? to Item 11?})) - 2)}{12} * 100$
		GLOBAL SATISFACTION	$\frac{((\text{Sum}(\text{Item 12 to Item 14}) - 3)}{14} * 100$	If either Item 12 or 13 is missing $\frac{((\text{Sum}(\text{Item 12? to Item 14?})) - 2)}{10} * 100$ If Item 14 is missing $\frac{((\text{Sum}(\text{Item 12 and Item 13})) - 2)}{8} * 100$

Abbreviations: eCOA = electronic clinical outcome assessment

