Recap of atopic eczema (RECAP)	Change from Baseline RECAP up to W16	Primary Estimand (Hybrid)	MMRM and BOCF	FAS	CCI [REDACTED] analysis: Change from Baseline RECAP up to W16

This document is confidential.

Measure	Variable	Estimand (Section 6)	Analysis Method (Section 6.3)	Population (Section 5)	Analysis Type
World Health Organisation – Five Well-Being Index (WHO-5)	Change from Baseline WHO-5 up to W16	Primary Estimand (Hybrid)	MMRM and BOCF	FAS	CCI analysis: Change from Baseline WHO-5 up to W16
Treatment Satisfaction Questionnaire for Medication-9 items (TSQM-9)	TSQM-9 up to W16	Primary Estimand (Hybrid)	MMRM and BOCF	FAS	CCI analysis: TSQM-9 up to W16
DLQI-Relevant (DLQI-R)	Change from Baseline DLQI-R up to W16	Primary Estimand (Hybrid)	MMRM and BOCF	FAS	CCI analysis: Change from Baseline DLQI-R up to W16

* The analyses of 4point NRS pruritus improvement will be based on those patients that had a baseline NRS pruritus score \geq 4points

The analyses of 4point DLQI improvement will be based on those patients that had a baseline DLQI score \geq 4points

The analyses of 4point NRS SKIN Pain improvement will be based on those patients that had a baseline NRS SKIN Pain score \geq 4points.

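### For TSQM-9, the SAP carries a pre-drug Day 1 satisfaction score forward as the Week 16 value, although the protocol plans description only

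*SAP*

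**What the plan says.** **Analysis in the SAP.** The summary table in SAP 9.6 has a row for "TSQM-9 up to W16". It assigns the primary (hybrid) estimand, a mixed model for repeated measures (MMRM) together with BOCF, and the full analysis set. SAP 6.1.2 gives the hybrid rules for continuous endpoints. Stopping for lack of efficacy (ICE2) and rescue or prohibited medication (ICE3) both lead to the value being set to baseline; stopping for other reasons (ICE1) leads to missing. SAP 6.3 names BOCF as the tool for the set-to-baseline cases.

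**Analysis in the protocol.** Protocol 11.8.2 states: "DLQI-R, RECAP, TSQM-9, and WHO-5 will all be analysed descriptively on the overall population". SAP Section 11, which lists departures from the protocol, does not mention this one. Protocol 11.2 lets the SAP prevail where the two differ.

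**Timing.** In the Induction schedule (Protocol Table 1, SAP 4.6), TSQM-9 is given on Day 1 and at Week 16 only. Protocol 10.1 puts patient-reported outcomes first at each visit and study drug last.

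**Scoring.** The protocol says "The TSQM-9 is a 9-item measure" (10.4.13). SAP 9.2 agrees: "Version 9 of the TSQM consists of 9 items that results in three specific domains". The same SAP row scores Effectiveness from Items 1 to 3, Convenience from "Item 9 to Item 11" and Global Satisfaction from "Item 12 to Item 14". It gives no key from those numbers to the form in use.

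**The concern.** For EASI or itch, setting a patient to baseline has a clear meaning: no improvement. TSQM-9 measures satisfaction with a medication, not a disease state. Its Day 1 answer is given before the first injection, so it must refer to something other than study drug. Carrying it forward does not say that the patient gained nothing; it substitutes a rating of a different treatment.

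The substitution is most awkward under ICE3. Protocol 9.9.4 keeps patients who use high-potency topical corticosteroid on study treatment and attending all visits. They can give a real Week 16 rating, and the plan replaces it.

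At stake is whether the reported Week 16 domain scores mean what their label says. Because the SAP prevails over the protocol, the modelled analysis with carry-forward is the one that would be run.

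**Working it through.** **1. What is carried forward.**
- Induction assessments: Day 1 and Week 16 (Protocol Table 1, SAP 4.6).
- Order on Day 1: questionnaire first, injection last (Protocol 10.1).
- Value after ICE2 or ICE3: baseline (SAP 6.1.2, 6.3).

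The Week 16 value for these patients is therefore a pre-drug score, and any difference from Day 1 is exactly 0. SAP 7.2.4 defines the baseline of questionnaires as a 7-day pre-treatment average. That does not fit a form completed once on Day 1, but it too would be pre-drug.

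**2. Effect on an arm mean.** Let r be the proportion of an arm with ICE2 or ICE3. The shift in the arm mean is

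r × (mean Day 1 score of these patients − mean Week 16 score they gave or would have given).

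Neither r nor either mean is in the documents, so the sign and the size are both unknown. To show scale only, assume 10–20% on placebo and 3–8% on lebrikizumab:

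| Arm | n | Assumed r | Patients with a carried score |
|---|---|---|---|
| Placebo | 104 | 10–20% | 10.4–20.8, about 10 to 21 |
| Lebrikizumab | 208 | 3–8% | 6.2–16.6, about 6 to 17 |

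These counts pool ICE2 and ICE3 and have no source in the plan.

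**3. Scope of the model.** SAP 6.1.2 and Protocol 11.8.1.1 reserve this analysis for continuous endpoints measured at several post-baseline Induction visits. TSQM-9 has one. The model could still be fitted, but it would reduce to a single-visit comparison adjusted for a Day 1 score that rates another treatment.

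**4. Protocol against SAP.**

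| Instrument | Protocol 11.8.2 | SAP 9.6 | Listed in SAP Section 11 |
|---|---|---|---|
| TSQM-9 | descriptive | MMRM with BOCF | no |
| DLQI-R | descriptive | MMRM with BOCF | no |
| RECAP | descriptive | MMRM with BOCF | no |
| WHO-5 | descriptive | MMRM with BOCF | no |

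The mismatch covers all four. The meaning of the carried value is a problem only for TSQM-9, because the other three rate the patient's own condition at both times.

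**5. Item numbers and divisors.** SAP 9.2 states that each domain runs from 0 to 100. The formulas use items 1, 2, 3, 9, 10, 11, 12, 13 and 14: nine distinct items in three sets of three. Let w be the range width of an item.
- Effectiveness and Convenience: three widths sum to 18 and any two to 12, so each w = 6.
- Global Satisfaction: w12 + w13 + w14 = 14, w12 + w14 = 10, w13 + w14 = 10, w12 + w13 = 8. Hence w13 = 14 − 10 = 4, w12 = 14 − 10 = 4 and w14 = 14 − 8 = 6.

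At the maximum, the formulas give 18/18, 18/18 and 14/14, each × 100 = 100. With every item at 1, they give (3 − 3) = 0. The missing-item versions (12/12, 10/10, 8/8) also reach 100. The stated range is reproduced and the divisors agree with one another.

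**The case against.** **The carried score may act as a reasonable failure value.** Inclusion criteria 6 and 7 require inadequate response to topical treatment and failure of, or unsuitability for, cyclosporine. Day 1 satisfaction may therefore be low, and BOCF may resemble a poor outcome. That is plausible, but it is not assured. Protocol 7.2.2 admits up to 60 patients with prior dupilumab, some of whom stopped for reimbursement or personal reasons. The Convenience domain also need not follow efficacy. The objection correctly rules out claiming a bias in a known direction.

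**BOCF may fill only missing values.** SAP 6.3.1 speaks of imputing missing data, and 6.3.1.1 ties BOCF to an intercurrent event of death that is not among ICE1 to ICE3. On that reading, an observed Week 16 rating after rescue would survive. However, the strategy table in 6.1.2 sets ICE3 values to baseline without that limit, and the hybrid estimand counts only success without rescue. The table is the better guide to intent.

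**The SAP prevails.** This is true under Protocol 11.2. It settles which method is run, not whether the method suits the scale or whether the departure was declared.

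**A stronger reading of the scoring.** A reader might infer from the item numbers that two of the three domains cannot be computed. On a form numbered 1 to 9, Convenience would find only Item 9 and Global Satisfaction nothing; the SAP has rules for one missing item only, and Items 4 to 8 would go unused. But no document says the form or the electronic dataset is numbered that way. Exactly nine items are named and the divisors are coherent, which fits a nine-item form whose items keep non-consecutive numbers.

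**Conclusion.** The carry-forward for TSQM-9 should be removed. After ICE2 or ICE3, the planned Week 16 value is a rating given before any study drug. For patients on high-potency topical rescue who remain on treatment, it displaces a usable Week 16 answer. The repeated-measures analysis is outside its own stated scope here and departs from the protocol without being declared.

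The conclusion rests on the visit schedule, on the order of procedures within a visit, and on reading the SAP 6.1.2 table as written. The number of patients affected and the direction of any bias cannot be derived from the documents. It would also go too far to infer that every affected patient failed study drug: that description fits ICE2, whereas ICE3 includes patients who continue.

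The consequence is minor. TSQM-9 is not a primary or key secondary endpoint in the protocol, and SAP 7.9 makes study success depend on the primary endpoint alone. The item numbering is a labelling gap, not a demonstrated loss of any domain.

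**What to change.** 1. **SAP 9.6, TSQM-9 row.** Replace the model and BOCF with the protocol's descriptive analysis: observed Week 16 scores for each of the three domains, by randomised arm, with no carry-forward from Day 1. Show the number of patients with and without a score in each arm.
2. **SAP 9.6, rows for DLQI-R, RECAP and WHO-5.** Reconcile them with Protocol 11.8.2. Either restore the descriptive analysis, or keep the model and record the change and its reason in SAP Section 11.
3. **SAP 9.2.** Add a key linking item numbers 1–3, 9–11 and 12–14 to the nine questions on the form used and to the electronic variable names. Leave the divisors as they are.

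The cost is SAP wording; no new data are needed. There would be no modelled TSQM-9 comparison, which the protocol did not plan. An observed-data summary leaves out patients without a Week 16 form, so it has to be read with the counts in item 1.

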9.3. Analysis of the Primary and Key Secondary Efficacy Endpoints

The primary and key secondary efficacy endpoints (for the main and second estimands) will be analysed by means of a Cochran-Mantel-Haenszel (CMH) model adjusted by country, age (adolescents/adults), prior use of dupilumab (yes/no), and Baseline severity of disease (IGA=3/IGA=4). If the model does not converge, country will be removed as an adjusting factor. The estimate of the adjusted common risk difference, with corresponding Mantel-Haenszel-Sato (Sato 1989) adjusted 2-sided 95% CI and p-value will be presented. Additionally, the CMH adjusted odds ratio along with the 95% two-sided asymptotic CI will be presented. The primary analysis will be based on the FAS which was defined as all randomized patients. When analysing the dupilumab naïve and previously exposed populations, the factor for prior use of dupilumab will be removed from the CMH adjustment.

Details are described in [Appendix 2](#). Details of Combining Estimates and Test Statistics for Categorical Endpoints with Multiple Imputation

Example code for CMH test:

CCI

This document is confidential.

For analyses using multiple imputation, the analysis will be conducted on the complete dataset, for each imputation separately. Modelled results will be combined using Rubin's rule (PROC MIANALYZE).

SAS Proc MIANALYZE will be used to combine the 100 point estimates (main estimand) for the difference in percentage of patients achieving EASI 75 response at Week 16 between treatments and standard errors, allowing appropriate statistical inference as described below:

CCI

The following sensitivity analysis will also be conducted for the main and second estimands of the primary and key secondary efficacy endpoints, on the overall population:

Analysis Set	Modelling Method	Estimand and Data Handling
Sensitivity Analysis Conducted on Main and Second Estimands		
PPS	CMH model adjusted by country, and stratification factors used in the randomisation (age, previous use of dupilumab, and Baseline severity of disease, as per primary analysis).	As per main and second estimands

Abbreviations: CMH = Cochran-Mantel-Haenszel; PPS = Per Protocol Set.

All inferential analyses of the primary and key secondary efficacy endpoints, including multiple imputation approaches will be conducted during the Induction Period only (eg, up to and including Week 16). During the Maintenance Period, only descriptive analyses will be performed for efficacy. The handling of estimands as detailed above will also only apply up to and including Week 16. After this point, data will only be analysed as observed.

In addition, to support efficacy analyses, a summary of the incidence of the ICEs at each visit up to Week 16 will be presented.

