Clinical Trial Protocol Title: A Randomised, Double-Blind, Placebo-Controlled Phase 3 Clinical Trial to Assess the Efficacy and Safety of Lebrikizumab in Combination With Topical Corticosteroids in Adult and Adolescent Patients With Moderate-To-Severe Atopic Dermatitis That Are Not Adequately Controlled With Cyclosporine or For Whom Cyclosporine is Not Medically Advisable.

Trial Code: M-17923-30

The individual signing this clinical trial protocol declares that he/she has reviewed it for completeness, accuracy. He/she is responsible for the trial and agrees to conduct it in adherence to the present document, any amendments, to ICH GCP guidelines, and to local regulatory requirements, wherever applicable.

Principal Investigator

Role	Name	Signature	Date
Principal Investigator	PPD		

1 Protocol Synopsis

Title:

A Randomised, Double-Blind, Placebo-Controlled Phase 3 Clinical Trial to Assess the Efficacy and Safety of Lebrikizumab in Combination With Topical Corticosteroids in Adult and Adolescent Patients With Moderate-To-Severe Atopic Dermatitis That Are Not Adequately Controlled With Cyclosporine or For Whom Cyclosporine is Not Medically Advisable.

Short Title:

Efficacy and safety of lebrikizumab in patients with atopic dermatitis (AD) not adequately controlled or non-eligible for cyclosporine.

Investigators:

A Principal Investigator will be designated at each participating clinical trial centre, and a Coordinating Investigator will be nominated among the participating sites. The name, address, and affiliation of each Principal Investigator and the Coordinating Investigator will be detailed in the final clinical study report.

Trial Centres:

This is an international multicentre study. The study is planned to be conducted at approximately 81 centres in approximately 9 countries within Europe, including the United Kingdom, Italy, France, Spain, Germany, the Netherlands, Belgium, Austria, and Poland.

Study Duration:

The duration of the entire study from first patient, first visit to last patient, last visit is anticipated to be approximately 24 months.

Duration of Treatment:

The duration of each patient's treatment is up to 52 weeks. The study has 2 treatment periods: a 16-week double-blind Induction Period followed by a 36-week open-label Maintenance Period.

Duration of Patients' Participation in the Trial:

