Eligible adult and adolescent (aged ≥ 12 to < 18 years and weighing ≥ 40 kg) patients with moderate-to-severe AD for at least 1 year, defined according to the Hanifin and Rajka Criteria,² an Eczema Area and Severity Index score (EASI) of ≥ 16 , an Investigator Global Assessment (IGA) score of ≥ 3 and a body surface area (BSA) affected by AD of $\geq 10\%$ will be enrolled (adolescent patients aged ≥ 12 to < 18 years will make up 12.5% of the overall population compared to adults aged ≥ 18 years). Eligible patients must have documented history of inadequate response to treatment with topical AD medication within 6 months before Screening, documented history of inadequate response or intolerance to CsA, or CsA-naïve patients for whom CsA treatment is not medically advisable. Patients with previous exposure to dupilumab, including suboptimal responses (eg, persistence of itch despite treatment with dupilumab, flare-up days before the next dupilumab dose) may be included in the study with a washout period of 8 weeks before Baseline. During this washout period, patients may be allowed to use TCS, which will need to be stopped at least 1 week before Baseline. The enrolment of this subpopulation of patients will be limited to a maximum of 60 enrolled patients. All other enrolled patients must be naïve to IL-4 or IL-13 blocking antibodies.

Test Investigational Medicinal Product, Dosage, and Mode of Administration:

Substance code/name:	Lebrikizumab
Administration route:	Subcutaneous (SC)
Unit dose/strength:	Each prefilled syringe is intended for a single 2 mL dose (250 mg)
Dosage form:	Solution for injection containing 125 mg/mL lebrikizumab. Supplied as a sterile prefilled syringe with a pre-assembled needle safety device (PFS-NSD).
Frequency:	During the 16-week Induction Period and 36-week Maintenance Period, 250 mg lebrikizumab Q2W (with loading doses of 500 mg [2 syringes] given at Baseline and Week 2 during Induction Period, and at Week 16 and Week 18 during the Maintenance Period for patients who

received placebo during the Induction Period). After completion of the Week 16 visit, patients will enter the Maintenance Period:

- Patients who received lebrikizumab 250 mg Q2W during the Induction Period will continue to receive lebrikizumab 250 mg Q2W during the Maintenance Period
- Patients who received placebo Q2W during Induction Period will start receiving lebrikizumab 250 mg Q2W (with loading doses at Week 16 and Week 18) during the Maintenance Period.

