The primary and key secondary endpoints (for the main and second estimands) will be analysed by means of a Cochran-Mantel-Haenszel (CMH) model adjusted by country, age (adolescents/adults), prior use of dupilumab (yes/no), and baseline severity of disease (IGA=3/IGA=4). The FAS will be the primary analysis set; if the model does not converge, country will be removed as an adjusting factor. The estimate of the adjusted common risk difference, with corresponding Mantel-Haenszel-Sato (Sato 1989)⁵⁸ adjusted 2-sided 95% CI and p-value will be presented. Additionally, the CMH adjusted odds ratio along with the 95% two-sided asymptotic CI will be presented.

For analyses using multiple imputation, the analysis will be conducted on the complete dataset, for each imputation separately. Modelled results will be combined using Rubin's rule (PROC MIANALYZE) for tabulation.

Sensitivity Analysis for the Primary and Key Secondary Efficacy Endpoints:

The following sensitivity analysis will also be conducted for the main and second estimands of the primary and key secondary efficacy endpoints, on the overall population:

Table 11. Sensitivity Analysis

Analysis Set	Modelling Method	Estimand and Data Handling
Sensitivity Analysis Conducted on Main and Second Estimands		
PPS	CMH model adjusted by country, and stratification factors used in the randomisation (age, previous use of dupilumab, and baseline severity of disease, as per primary analysis).	As per main and second estimands

Abbreviations: CMH = Cochran-Mantel-Haenszel; PPS = Per Protocol Set.

Additional subgroup analyses based on baseline characteristics will be presented as appropriate using forest plots.

All inferential analyses of the primary and key secondary efficacy endpoints, including multiple imputation approaches, will be conducted during the Induction Period only (eg, up to and including Week 16). During the Maintenance Period, only descriptive analyses will be performed for efficacy. The handling of estimands as detailed above will also only apply up to and including Week 16. After this point, data will only be analysed as observed.

B. All Other Secondary and Other Efficacy Endpoints

All binary other secondary and other efficacy endpoints will be analysed using the same methodology as described above for the primary efficacy endpoint using only the main estimand. Sensitivity analyses based on the PPS population will not be conducted for these endpoints.

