4.3. Determination of Sample Size

The study is designed to gain an estimate of the effect of study treatment in the patient population of adults and adolescent patients not adequately controlled with cyclosporine or for whom cyclosporine is not medically advisable. The sample size for this study has been estimated to allow power enough to show efficacy in the overall study population for the primary and key secondary endpoints.

A total sample size of 312 patients, in a 2:1 ratio (208 lebrikizumab arm and 104 placebo arm) will provide more than 95% nominal power to detect a statistically significant difference of 25% (55% lebrikizumab arm versus 30% placebo arm) in the primary study endpoint: proportion of patients achieving EASI 75 at Week 16. As reference and considering independence between variables, this same sample size will also provide more than 90% overall power to also detect a difference of 18% (30% lebrikizumab arm versus 12% placebo arm) in the proportion of patients achieving IGA (0/1) at Week 16 and of 34% differences (43% lebrikizumab arm versus 9% placebo arm) in the proportion of patients achieving a 4-point pruritus numerical rating scale (NRS) decrease from Baseline at Week 16. A two-sided type one error of 5% has been assumed.

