7.5. Adjustments for Covariates

Unless otherwise specified, the statistical analysis models for the Induction Period efficacy and health outcome analysis will include the following stratification factors for Baseline randomization: age (adolescent patients 12 to <18 versus adults ≥18 years) and baseline disease severity (IGA=3 versus IGA=4). Additionally, the following factors will be included in the models:

- Country of patient as recorded at screening
- For analyses of the full population (i.e. not the subgroups of dupilumab naïve or previously exposed patients), the stratification factor of prior use of dupilumab (yes/no) will be included.

If the model does not converge, country will be removed as a factor from the specific model.

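### The primary CMH analysis crosses country with the three randomisation factors, giving up to about 72 strata for 312 patients, and the rule for dropping country cannot operate

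*SAP*

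**What the plan says.** **Analysis model.** SAP 9.3 and Protocol 11.8.1.1 adjust the CMH analysis of the primary and key secondary endpoints for country, age group, prior dupilumab and baseline IGA. They report a Mantel-Haenszel risk difference with Sato interval and a CMH odds ratio. The per-protocol sensitivity analysis uses the same factors.

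**Rule for dropping country.** SAP 9.3: "If the model does not converge, country will be removed as an adjusting factor". Protocol 11.8.1.1: "if the model does not converge, country will be removed as an adjusting factor". SAP 7.5 states it for all Induction Period models: "If the model does not converge, country will be removed as a factor from the specific model".

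**Randomisation.** Protocol 9.6.2 and SAP 4.1.2 stratify by prior dupilumab, age group and IGA 3 or 4. Country is not a factor.

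**Size and mix.** The trial has "312 patients, in a 2:1 ratio (208 lebrikizumab arm and 104 placebo arm"), at "approximately 81 centres in approximately 9 countries within Europe", of which the Protocol Synopsis names nine. Adolescents are to be 12.5% of patients. On prior dupilumab: "The enrolment of this subpopulation of patients will be limited to a maximum of 60 enrolled patients".

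**Computation.** SAP 9.3 refers to Appendix 2 for details. Appendix 2 uses PROC FREQ with the strata crossed in the TABLES statement, but lists geographic region, age group and severity, without prior dupilumab.

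Neither document gives a pooling rule for sparse strata, expected enrolment by country, or the expected IGA split.

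**The concern.** A convergence condition makes sense for an iterative fit such as the MMRM or Cox model. The CMH quantities are sums over strata and involve no iteration, so the condition can never be met, however sparse the table becomes. Country therefore always stays in, unless someone reads the clause loosely and removes it at their own discretion. If that happened after unblinding, it would be a choice between two primary results.

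Meanwhile, patients in a cell with only one arm add nothing to the risk difference, odds ratio or test. Small groups spread over many cells lose most, and here those are the adolescents and the dupilumab-exposed. Multiple imputation does not help, because stratum membership is the same in all 100 datasets. The per-protocol analysis shares the factor list, so it would not show the effect either. At stake are precision and how well the estimate represents the randomised population.

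**Working it through.** **1. Reproduce the stated power.** SAP 4.3 claims "more than 95% nominal power to detect a statistically significant difference of 25" percentage points, and more than 90% overall power with both key secondary endpoints, under independence. It adds: "A two-sided type one error of 5% has been assumed".

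Power = Φ[(Δ − 1.96·SE₀)/SE₁], with SE₀ from the pooled proportion and SE₁ from the separate proportions; n = 208 and 104.

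- EASI 75, 55% v 30%: pooled (114.4 + 31.2)/312 = 0.467; SE₀ = 0.0599; SE₁ = 0.0566; z = (0.25 − 0.1174)/0.0566 = 2.34; power 99.0%.
- IGA, 30% v 12%: pooled 0.24; SE₀ = 0.0513; SE₁ = 0.0450; z = (0.18 − 0.1005)/0.0450 = 1.77; power 96.1%.
- Pruritus, 43% v 9%: above 99.9%.
- Joint: 0.990 × 0.961 × 1.000 = 95.2%.

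Both claims hold before stratification is considered.

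**2. Why one-arm cells drop out.** With n₁ₖ and n₀ₖ patients and response proportions p₁ₖ and p₀ₖ in stratum k, the Mantel-Haenszel risk difference is Σwₖ(p₁ₖ − p₀ₖ)/Σwₖ, where wₖ = n₁ₖn₀ₖ/(n₁ₖ + n₀ₖ). If either arm is empty, wₖ = 0. The terms of the odds ratio, CMH statistic and Sato variance vanish likewise.

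**3. Sparsity.**

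- Strata: 9 × 2 × 2 × 2 = 72, so 312/72 = 4.3 patients per cell on average. The randomisation has 8 strata, so 39 per stratum.
- Adolescents: 12.5% of 312 = 39, over 9 × 2 × 2 = 36 cells, about 1.1 per cell.
- Dupilumab-exposed at the cap: 60/36 = 1.7 per cell.
- Chance that a cell of m patients holds one arm only, under independent 2:1 allocation: (2/3)^m + (1/3)^m. This is 100% for m = 1, 56% for 2, 33% for 3 and 21% for 4.

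**4. Simulation.** 312 patients, 39 adolescents, 2:1 permuted blocks within the 8 randomisation strata, then cross-classification by country. The documents do not give country shares, IGA 4 share (30-50% tried), block size or number exposed, so these are assumptions. There were 600 runs per setting and 1,500 for the row without country.

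| Setting | FAS at zero weight | Adolescents | Exposed | Mean SE |
|---|---|---|---|---|
| Country dropped (8 strata) | 0.3% | 2.3% | 1.5% | 0.0565 |
| 9 equal countries, 60 exposed | 11.7-11.9% | 49-52% | 33-35% | 0.0617-0.0619 |
| Moderately uneven, 60 exposed | 11.3-11.5% | 44-47% | 30-31% | 0.0613-0.0616 |
| Skewed, 60 exposed | 10.0-10.3% | 36-37% | 24% | 0.0605-0.0609 |
| Very skewed, 60 exposed | 9.5-9.7% | 31-32% | 22% | 0.0604-0.0605 |
| Equal, 30 exposed | 10.5% | 46% | 55% | 0.0613 |
| Skewed, 30 exposed | 9.3% | 32% | 39% | 0.0605 |
| Appendix 2 strata, region read as country (36 cells) | 5.1% | 37% | - | 0.0596 |

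Simple randomisation with equal countries gives 12.6% of the FAS and 54% of adolescents. Six contributing countries instead of nine give about 7% of the FAS.

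Standard error: 0.0604/0.0565 = 1.07 and 0.0618/0.0565 = 1.09. Put as information, a loss of 11-16% gives 1/√0.89 = 1.06 to 1/√0.84 = 1.09.

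**5. Operating characteristics with country kept, and no country effect on response.**

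- EASI 75 power is about 97-99%.
- IGA power is about 93%, so joint power is about 0.973 × 0.93 = 90%. Across settings it is about 90-92%. The lowest CMH result was 89.4% (equal countries); Wald tests with the Sato variance gave 91-93%. None of these allows for missing data.
- Type I error is 5.4% with country and 4.6% without (3,000 runs each).
- The mean estimated difference is 0.244-0.255 against a true 0.25.

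**The case against.** **Adjusting for country is a legitimate choice in a multinational trial.** This stands. The standard-error penalty shrinks if country is prognostic: with nine equal countries it is about 9-10% with no country effect, 7% with a between-country SD of 0.5 on the logit scale, and 1% with an SD of 1.0. But this defends having country in the analysis; it does not defend full crossing with a fallback that cannot fire.

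**The 72 strata are not certain.** This also stands. Appendix 2 lists other factors, the example CMH code is redacted, and the country count is approximate; four contributing countries would bring the FAS share down to about 4%. The protocol names nine, however, and Appendix 2's list, with region read as country, still leaves about 5% of the FAS and 37% of adolescents at zero weight.

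**No stated claim fails.** For the primary endpoint this is right. SAP 7.9 makes success depend on that endpoint alone, and the joint figure is offered only for reference. The dupilumab subgroups carry no power claim.

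A reader might infer that a known share, such as a ninth of the FAS and half of the adolescents, is lost. The documents do not support fixed figures. The adolescent share in particular depends on how evenly countries enrol, and about half needs near-even enrolment.

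**Conclusion.** The point holds as a defect of specification with a moderate cost in precision and representation. The convergence rule is inoperable for the CMH analyses whatever is assumed. The size rests on assumed country shares, IGA split and dupilumab count: about 7-13% of the FAS, roughly 30-55% of adolescents and about 20-55% of exposed patients at zero weight, with a standard error about 6-9% larger if country matters little. The exposed share carries over to the dupilumab-exposed subgroup analysis, where the cells are the same.

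A reader might also infer that the trial is underpowered or the primary test invalid. Neither follows. Primary power remains above the stated 95%, and joint power moves to the edge of the stated 90% without clearly breaking it. Type I error is near nominal, and bias is negligible under a constant effect. Under-weighting adolescents would shift the estimate only if the effect differs by age, and Protocol 7.2.2 expects similar efficacy.

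This should be corrected before unblinding. It does not undermine the trial.

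**What to change.** - Stratify the CMH test, Mantel-Haenszel risk difference and odds ratio by the three randomisation factors only: age, prior dupilumab and IGA (age and IGA within the dupilumab subgroups). In the simulation this leaves 0.3% of the FAS at zero weight.
- Delete the convergence clause for CMH analyses. Keep it for the MMRM and Cox models.
- Align SAP 7.5, SAP 9.3 with its per-protocol table, and Appendix 2 on this one list, and record the change from the protocol in SAP Section 11.
- Keep the country-stratified analysis as supportive, and report how many patients fall in one-arm strata, overall and for adolescents and dupilumab-exposed patients.

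The cost is wording and a small programming change. Protocol 11.2 lets the SAP prevail where the two differ. The small downside is that the main estimate is no longer adjusted for country, which matters more if country turns out to be strongly prognostic.
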